### STUDY SUMMARY

TITLE	Randomized Controlled Clinical Outcomes of the Vanguard XP Bicruciate Knee System
DESIGN	Prospective Controlled Multi-Center
PURPOSE	Compare the clinical outcomes of the Vanguard XP Bicruciate Total Knee System to the Vanguard CR Total Knee System
OUTCOME MEASURES	Patient Perception of recovery, Operative Room Procedure Time, Intraoperative complications; Anterior Cruciate Ligament (ACL) status; knee stability; readmissions, adverse events, pain, patient satisfaction, quality of life
POPULATION	306 knees, 5 surgeons
ELIGIBILITY	Patients will be included according to FDA cleared labeling of device in accordance with indications and contraindications for use.
DURATION	The study is anticipated to last no longer than 12 years which will include time for enrollment, data collection through ten years of follow-up and data analysis.

**1. INTRODUCTION****1.1. BACKGROUND**

Early experiences with the Vanguard XP knee have been promising, with positive feedback on the early evaluation surveys. A randomized controlled trial is required to compare the clinical and patient reported outcomes with the Vanguard CR knee, which is well established. This study is designed to compare the clinical outcomes in patients who receive the Vanguard XP Knee System and patients who receive the Vanguard CR Femur with CR Bearing.

**1.2. DEVICE DESIGN AND DESCRIPTION**

Both knee systems included in this trial have been 510(k) cleared by the United States Food and Drug Administration (FDA). Both systems have the same indications for use (see section 3.1). The main difference between these total knee systems is that the Vanguard XP system requires a functional Anterior Cruciate Ligament (ACL), and the Vanguard CR system requires the anterior cruciate ligament to be sacrificed. Therefore the Vanguard XP Knee System is constrained by natural soft tissue, and the Vanguard CR is constrained by soft tissue and device design. Both systems allow the surgeon to retain the posterior cruciate ligament. Biomet knee joint replacement components include femoral, tibial, and patellar components. Components are available in a variety of designs and size ranges intended for both primary and revision applications. Specialty components are available including; femoral stems, femoral augments, tibial stems, tibial augments, tibial cement plugs and tibial screws.

For purposes of this study, in order to reduce variables with randomization, only patients receiving a primary total knee with a functional ACL will be enrolled. If the ACL is deemed not functional (either preoperatively or intraoperatively), the patients will be treated according to local standard of care and will not be enrolled into this study. A chart comparing the devices is provided:

**Table 1.2-A**

Device Comparison	Vanguard XP Knee System	Vanguard CR Knee System																				
Picture																						
Regulatory Status	FDA 510(k) Cleared	FDA 510(k) Cleared																				
Basic Materials*	
  
 Components	Materials	
   
 Femoral Components	CoCrMo Alloy	
 
 Tibial Plates	CoCrMo Alloy	
 
 Tibial Bearings	Ultra-High Molecular Weight Polyethylene (UHMWPE) <math>\alpha</math> – tocopherol	
 
 Patellas	UHMWPE/Titanium Alloy/316LVM Stainless Steel	
  
	Components	Materials	Femoral Components	CoCrMo Alloy	Tibial Plates	CoCrMo Alloy	Tibial Bearings	Ultra-High Molecular Weight Polyethylene (UHMWPE) $\alpha$ – tocopherol	Patellas	UHMWPE/Titanium Alloy/316LVM Stainless Steel	
  
 Components	Materials	
   
 Femoral Components	CoCrMo Alloy / Titanium Alloy	
 
 Tibial Plates	CoCrMo Alloy / Titanium Alloy	
 
 Tibial Bearings	Ultra-High Molecular Weight Polyethylene (UHMWPE)	
 
 Patellas	UHMWPE/Titanium Alloy/316LVM Stainless Steel	
  
	Components	Materials	Femoral Components	CoCrMo Alloy / Titanium Alloy	Tibial Plates	CoCrMo Alloy / Titanium Alloy	Tibial Bearings	Ultra-High Molecular Weight Polyethylene (UHMWPE)	Patellas	UHMWPE/Titanium Alloy/316LVM Stainless Steel
Components	Materials																					
Femoral Components	CoCrMo Alloy																					
Tibial Plates	CoCrMo Alloy																					
Tibial Bearings	Ultra-High Molecular Weight Polyethylene (UHMWPE) $\alpha$ – tocopherol																					
Patellas	UHMWPE/Titanium Alloy/316LVM Stainless Steel																					
Components	Materials																					
Femoral Components	CoCrMo Alloy / Titanium Alloy																					
Tibial Plates	CoCrMo Alloy / Titanium Alloy																					
Tibial Bearings	Ultra-High Molecular Weight Polyethylene (UHMWPE)																					
Patellas	UHMWPE/Titanium Alloy/316LVM Stainless Steel																					

*Please consult the package insert for a complete list of FDA cleared component materials and risk analysis for each device.
																						
Indications	Painful and disabled knee joint resulting from osteoarthritis, rheumatoid arthritis or traumatic arthritis where one or more compartments are involved; Correction of varus, valgus, or posttraumatic deformity; or Correction or revision of unsuccessful osteotomy, arthrodesis, or failure of a previous joint replacement procedure.	Painful and disabled knee joint resulting from osteoarthritis, rheumatoid arthritis or traumatic arthritis where one or more compartments are involved; Correction of varus, valgus, or posttraumatic deformity; or Correction or revision of unsuccessful osteotomy, arthrodesis, or failure of a previous joint replacement procedure.																				
Contra indications	Infection, Sepsis, Osteomyelitis;  Relative contraindications include: Uncooperative patient or patient with neurologic disorders who is incapable of following directions; Osteoporosis;	Infection, Sepsis, Osteomyelitis;  Relative contraindications include: Uncooperative patient or patient with neurologic disorders who is incapable of following directions; Osteoporosis;																				

Device Comparison	Vanguard XP Knee System	Vanguard CR Knee System
	Metabolic disorders which may impair bone formation; Osteomalacia; Distant foci of infections which may spread to the implant site; Rapid joint destruction, marked bone loss or bone resorption apparent on roentgenogram; Vascular insufficiency, muscular atrophy, neuromuscular disease; Incomplete or deficient soft tissue surrounding the knee.	Metabolic disorders which may impair bone formation; Osteomalacia; Distant foci of infections which may spread to the implant site; Rapid joint destruction, marked bone loss or bone resorption apparent on roentgenogram; Vascular insufficiency, muscular atrophy, neuromuscular disease; Incomplete or deficient soft tissue surrounding the knee.

### **1.3. RATIONALE FOR CURRENT STUDY**

There is an increasing demand for joint replacement in a younger population(1). Due to the changing demographics of joint replacement, the younger population is seeking options that not only correct their disease or deformity, but do not limit them in activity. Activities of daily living are higher in this patient group, and patients needing total joint replacement do not have many options that accommodate this level of activity.

It is assumed that with preservation of ligaments, the knee will have more normal kinematics and therefore increased functional ability post-operatively, in comparison to traditional TKA that sacrifices soft tissue and stabilizes the knee with the device. There may be other advantages with preserving natural soft tissue that will be explored in a larger study, including restoration of natural kinematics, lower rate of loosening and polyethylene wear. This study will focus on knee stability, alignment of components, patient satisfaction, quality of life, intraoperative complications, re-admissions, and long-term survivorship.

### **1.4. PURPOSES**

- A. Compare patient perception of their knee implant feeling “normal / asymptomatic.”
- B. Compare clinical outcomes through 2 year standard of care follow-up.
- C. Evaluate patient perceived clinical outcomes and survivorship through 10-years of follow-up.

## **2. STUDY DESIGN**

### **2.1. OVERALL DESIGN**

Prospective Randomized Controlled clinical outcome study based in the United States.

**2.2. STUDY GROUPS/TREATMENTS****A. Arm 1 (Control) : Vanguard CR Total Knee System**

Patients who receive the cemented Vanguard CR femur with Vanguard CR Bearing based on meeting indications for use, and inclusion / exclusion criteria described in the protocol.

**B. Arm 2: Vanguard XP Total Knee System**

Patients who receive the cemented Vanguard XP BiCruciate Knee System based on meeting indications for use, and inclusion / exclusion criteria described in the protocol.

**2.3. NUMBER OF SITES AND SUBJECTS/PROCEDURES**

A total of 306 cases (knees) will be included in this study from four centers; 153 Vanguard CR and 153 Vanguard XP. Sample size calculation is provided in Section 8.1.

**2.4. RANDOMIZATION**

Patients will be randomized using a 1:1 blocked randomization scheme. Bilateral patients should be randomized by knee. Randomization will occur by enrolling the patient into Joint Assist and assigning an operative date. At that point the electronic database will assign the treatment group for the patient. The patient will be blinded from treatment until surgery has occurred.

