**2.5. PRIMARY AND SECONDARY ENDPOINTS**

- A. Primary Endpoint: Percentage of patients reporting their knee feels “normal”.
- B. Secondary Endpoints: Patient Reported Outcome Measures “PROMs”, Knee Society Score, Complication Rate, Pain Relief, Functional outcomes, Survivorship

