**C. Center Level Information**

1. **Patient Expectations of Knee Replacement Recovery\***
  - a. Each center's standard of care method for managing patient expectations for total knee replacement recovery will be documented and sent to the sponsor.
2. **Patient Rehabilitation\***
  - a. Each center's standard of care method for patient post-operative rehabilitation for total knee replacement recovery will be documented and sent to the sponsor.

*\*Not a research intervention, will be used for data analysis only. Not patient level data, and should be a summary of what is done as standard of care for all total knee patients at the center.*

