**F. Clinical Outcomes**

1. Data to determine the clinical and functional performance of the device will be collected. Pre-operative and post-operative analysis will be compared using recognized and validated systems:
  - a. **Modified Knee Society Score**
    - i. The American Knee Society Score is part clinical exam and part patient administered assessment of the knee. The objective part of the score, also known as the "knee score," should be collected in the clinic by qualified personnel. The functional and pain scores can be collected in

the clinic or via phone or mailer. An additional assessment of the incidence of “anterior knee pain” has been added to this CRF as an exploratory endpoint but does not affect the score. The full score will be collected preoperatively and at each post-operative visit through 2-years. After the 2-year visit, the patient administered portion will be collected with the PROMS Questionnaire by phone, email, or mailer from the patient.

b. Patient Reported Outcome Measures “PROMS”

- i. A PROMS Questionnaire will be completed by the patient before surgery, and at each postop appointment indicated in the data collection table to assess the patient’s perception of their knee replacement. This survey can be collected in the office, over the phone, or via mailer. The preoperative questionnaire contains the SANE, EQ-5D, Oxford Knee Score, and KOOS (The FJS and Patient Satisfaction questionnaires are only completed post-operatively). The postoperative questionnaire contains the SANE, Patient Satisfaction, FJS, EQ-5D, Oxford Knee Score, and KOOS validated patient administered outcomes scores.

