**2.8. ALLOWED WINDOW OF EACH SCHEDULE**

## A. Allowed Window of Each Schedule:

1. Discharge: 0-12 weeks
2. 6 months (+/- 2 weeks)
3. 1 year (+/- 2 months)
4. 2 years (+/- 2 months)
5. 3 years (+/- 2 months)
6. 5 years (+/- 2 months)
7. 7 years (+/- 2 months)
8. 10 years (+/- 2 months)

B. Each follow-up visit time point will be determined based on the date of surgery. All efforts should be made to bring patients back within the follow-up windows. Because this is a post-market study long-term study, patient visits that fall outside of window are allowable and will not be considered protocol deviations. The impact of the visit date will be assessed during data analysis.

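### No patient blinding is specified for any post-operative assessment, although the primary endpoint is the patient's own report that the knee feels normal

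*Combined protocol and SAP*

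**What the plan says.** On blinding, Section 2.4 has one sentence: "The patient will be blinded from treatment until surgery has occurred". The protocol does not describe blinding of patients after surgery, blinding of staff who collect scores, or any check of what patients believe they received.

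Section 2.5 defines the primary endpoint as "Percentage of patients reporting their knee feels" normal, and gives no time point. Section 2.7 F describes a patient-completed questionnaire, given before surgery and at the scheduled post-operative visits, "to assess the patient’s perception of their knee replacement". It adds: "The FJS and Patient Satisfaction questionnaires are only completed post-operatively". Section 2.8 opens the post-operative schedule with "Discharge: 0-12 weeks". Section 2.6 continues the questionnaire to 10 years and allows it to be completed in the office, by phone or by mail.

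Section 8.2 tests the primary endpoint with an unadjusted two-sided Pearson chi-square test at 0.05. No sensitivity analysis for reporting bias is planned.

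**The concern.** Whether a knee feels normal is a judgement only the patient can make, and there is no objective measurement behind it. Such an outcome is exposed to what the patient expects of the implant, and randomization does not balance an expectation that arises from learning the assignment.

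The documents give reasons why expectation might differ by arm. Section 1.1 says "Early experiences with the Vanguard XP knee have been promising", while the CR knee is described as well established. Section 1.3 assumes that preserving the ligaments gives more normal knee motion, which is close to the wording of the endpoint. If patients take in the same message, those who know they have the ligament-retaining knee may lean toward the answer being counted. They may equally expect more and be harder to satisfy. Bilateral patients randomized by knee could compare two implants whose identity they know.

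At stake is how the primary result is read. A difference could partly reflect knowledge of the implant, and the absence of one could partly reflect disappointed expectation. The post-operative patient-reported secondary endpoints share the exposure.

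**Working it through.** **Step 1: when the blind applies.**

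| Assessment | Timing | Under the stated blind? |
|---|---|---|
| Baseline SANE, EQ-5D, Oxford, KOOS and Knee Society Score | Pre-operative (Sections 2.6, 2.7 F) | Yes |
| Primary endpoint: knee feels normal | Necessarily after surgery | No |
| Forgotten Joint Score, satisfaction | Post-operative only (2.7 F) | No |
| All later questionnaires, to 10 years | 0-12 weeks onward (2.6, 2.8) | No |

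**Step 2: reproduce the plan's sample size.** Inputs from Section 8.1: proportions 0.66 and 0.83, two-sided alpha 0.05, power 90%, normal approximation. With pooled variance under the null and mean proportion 0.745:

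n = [1.960·√(2·0.745·0.255) + 1.282·√(0.66·0.34 + 0.83·0.17)]² / 0.17² = 136.05, rounded up to 137 per arm.

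Power at 137 is 90.2%. Allowing for 10% loss, 137/0.9 = 152.2, rounded up to 153 per arm and 306 in total. The plan's figures reproduce and are not in dispute.

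**Step 3: effect of a pure reporting shift.** Assume the implants are equal (0.66 in both arms) but reports of normal in the XP arm are raised by b. With p1 = 0.66, p2 = 0.66 + b and p̄ their mean:

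- s0 = √(2·p̄(1−p̄)/n)
- s1 = √([p1(1−p1) + p2(1−p2)]/n)
- P(reject) = Φ((b − 1.96·s0)/s1) + Φ((−b − 1.96·s0)/s1)

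Example, b = 0.10 and n = 137: s0 = 0.05483 and s1 = 0.05449. The first term is Φ((0.10 − 0.10746)/0.05449) = Φ(−0.137) = 0.446, and the second is negligible.

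| Assumed shift toward XP (points) | Rejection rate, 137 per arm | Rejection rate, 153 per arm |
|---|---|---|
| 0 | 5.0% | 5.0% |
| 3 | 8.3% | 8.7% |
| 5 | 14.4% | 15.6% |
| 8 | 30.3% | 33.2% |
| 10 | 44.6% | 48.7% |
| 12 | 60.0% | 64.8% |
| 15 | 80.7% | 84.8% |

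A larger sample does not help; it makes a biased difference more likely to reach significance.

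**Step 4: the observed difference needed.** With 90 of 137 control patients reporting normal, 105 of 137 in the XP arm is the smallest count giving p < 0.05, a difference of 15/137 = 10.9 points. At 153 per arm it is 117 against 101, or 16/153 = 10.5 points.

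**Step 5: the opposite direction.** Suppose the planned 17-point benefit is real but a reporting shift of 5 points runs against XP. The expected difference is then 17 − 5 = 12 points, and power at 137 per arm falls from 90.2% to 60.0%. A 7-point shift leaves 10 points and 44.6% power.

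**The case against.** **A reader might infer that patients are told their assignment once surgery is over.** The text does not say so. It fixes when blinding stops being required and describes no act of disclosure. The consent text was not available, so what patients learn afterwards cannot be checked. What stands is that nothing protects the assignment after surgery.

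**A reader might infer that the blind protects no measurement.** It does: baseline questionnaires and the Knee Society Score are collected under it. It also guards against patients leaving on learning their assignment before the first bony cut, when Section 3.3 allows replacement. The gap concerns post-operative outcomes only.

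**A reader might infer that a positive result would be an expectation effect.** The documents give neither size nor direction for one. The 45% figure needs a 10-point reporting shift, which is 10/17 = 59% of the planned effect; at 3 points the rate is about 8%.

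**A reader might take Section 2.7 C as an admission of the bias.** Each center's "method for managing patient expectations for total knee replacement recovery will be documented and sent to the sponsor", with the note "Not a research intervention, will be used for data analysis only". That shows interest in expectation. However, it is a center-level summary covering all total knee patients, so it neither demonstrates nor can correct a difference between arms within a center.

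**Practical limits.** This is a post-market comparison of two cleared devices. Implant cards, records and review of radiographs will reveal some assignments, and withholding the identity of a permanent implant is a matter for consent and the IRB. These points limit how complete a blind can be. They do not explain ending it at surgery, and the documents give no reason for that choice. Both arms are cemented total knees with the same indications, and questionnaires can be returned by mail.

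**Conclusion.** The concern holds in this form: the plan specifies no patient blinding during any assessment that can supply the primary endpoint, and that endpoint is a subjective self-report. Knowledge of the implant could bias the comparison in either direction.

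The size is illustrative. If the implants are equal at 66% and 137 patients per arm are analysed, reporting shifts of 3 to 10 points toward XP raise the rejection rate from 5% to between about 8% and 45%. A 5-point shift against XP would cut power for the planned 17-point difference from about 90% to 60%. These results rest on the assumed shifts and on the proportions in Section 8.1. They do not show that a bias exists.

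The trial can run as written. This is a worthwhile, low-cost improvement to the credibility of its main result.

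**What to change.** - **Extend the blind.** Change Section 2.4 so that patients remain blinded until they have completed the questionnaire that supplies the primary endpoint, at the time point the sponsor fixes for that endpoint. Section 2.5 states none. Two years, the last scheduled clinic assessment, is one option and is an assumption here.
- **Control disclosure.** Site staff do not volunteer the assignment. It is disclosed if the patient asks or if clinically needed, and the date is recorded.
- **Ask early.** At the first post-operative visit (0-12 weeks), before the outcome is established, ask which implant the patient believes they received. A guess taken only at the end would be confounded with outcome, because patients with good knees may assume they have the newer device. Report guesses and disclosure dates by arm, descriptively.
- **Leave the primary analysis in all randomized patients with data.** Do not use the still-blinded patients as a test of bias. That subset is selected after randomization and may differ by arm and by outcome.

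The cost is a short change to Section 2.4, one added consent sentence with IRB review, one question, one recorded date and a descriptive table. No extra staff or procedures are needed and the sample size does not change. The downside is that the blind will be partial, because implant cards, records and radiograph review will reveal some assignments.

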**2.5. PRIMARY AND SECONDARY ENDPOINTS**

- A. Primary Endpoint: Percentage of patients reporting their knee feels “normal”.
- B. Secondary Endpoints: Patient Reported Outcome Measures “PROMs”, Knee Society Score, Complication Rate, Pain Relief, Functional outcomes, Survivorship

## 2.6. ASSESSMENT PROCEDURE

**Table 2.6-A**

Form	Pre-op (screening)	Operative (Enrollment)	Discharge	3 Mos	6 Mos	1 Yr	2 Yrs	3 Yrs	5 Yrs	7 Yrs	10 Yrs
Screening Log	X										
Informed Consent	X										
Demographics / Medical History	X										
Operative Form		X									
Modified Knee Society Score*	X		X	E†	SC***	X	X				
PROMS** Questionnaire	X		X	E†	SC***	X	X	X	X	X	X
Radiographs: AP, ML, Skyline			X	E†	SC***	X	X				
Radiographic Form			X			X	X				
Adverse Events		AS NEEDED	AS NEEDED	AS NEEDED	AS NEEDED	AS NEEDED	AS NEEDED	AS NEEDED	AS NEEDED	AS NEEDED	AS NEEDED
Withdrawals		AS NEEDED	AS NEEDED	AS NEEDED	AS NEEDED	AS NEEDED	AS NEEDED	AS NEEDED	AS NEEDED	AS NEEDED	AS NEEDED
Protocol Deviations		AS NEEDED	AS NEEDED	AS NEEDED	AS NEEDED	AS NEEDED	AS NEEDED	AS NEEDED	AS NEEDED	AS NEEDED	AS NEEDED

\*Modified Knee Society Score includes an additional assessment of incidence of anterior knee pain. This additional question is exploratory and will not affect the total score of the KSS. In the event that a patient does not return for a visit, a partial “Phone Knee Society Score” can be completed and entered into the database.

\*\*Patient Administered Outcome Scores “PROMS” Questionnaire can be collected in the office, over the phone, or via mailer. The questionnaire contains SANE/Patient Satisfaction, Oxford Knee Score, EQ-5D, KOOS, and the Forgotten Joint Score validated patient administered outcomes scores. These scores are combined into the paper version for easier administration to patients for completing. When entering to Joint Assist, these scores will be separated but contain the same exact questions.

\*\*\*SC: 6 Month visit should be collected only if standard of care. Radiographs should be taken if standard of care at the center, however no radiographic form will be collected. Any adverse event or failure determined from radiographs should be documented on an adverse event form. All visits will be documented relative to the clinical site in the approved informed consent.

†"E" = exploratory and not required. If centers choose to collect 3-month data, they may although it is not required of this protocol. It should only be collected at centers where it is standard of care as an exploratory measure. Biomet will not reimburse for this milestone, but will allow data storage for centers that choose to document this to follow all standard of care visits. If this visit is followed, it must be included in the informed consent.

